3.1 Methodological Approach

The *Prehab* comprehensive inter-disciplinary program is intended to intervene to decrease frailty in high-risk elderly patients undergoing cardiac surgery.

Knowledge Gap – Will *Prehab* work in the frail, elderly?

Cardiovascular prevention and rehabilitation is a well-established and proven standard of care to decrease morbidity and mortality in patients with established and unrepaired cardiac disease.(4)(5)(6)(7)(8) In a landmark study by Arthur et al, 249 low-risk patients awaiting elective *CABG* were randomized either to an eight-week preoperative cardiac pre-habilitation (*Prehab*) program or to the usual care.(22) *Prehab* patients completed 2 exercise sessions per week and attended education classes on risk factor modification. These patients experienced shorter intensive care unit (*ICU*) and hospital lengths of stay (*LOS*) post-operatively and an improved quality of life compared to the controls, which persisted for 6 months following surgery. However, while this seminal study demonstrated the potential benefits of a “*Prehab*” program, this study was performed in younger, lower-risk patients and therefore did not address the needs of the frail, elderly patients currently being referred for cardiac surgery.

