3.3 Eligibility Criteria

3.3.1 Inclusion Criteria (all need to be fulfilled for eligibility)

- 1) Patients, aged 60 years or older, undergoing elective isolated coronary artery bypass grafting (*CABG*), aortic valve repair/replacement for moderate aortic stenosis or severe regurgitation, mitral valve repair/replacement for moderate stenosis or severe regurgitation or combined *CABG*/valve procedures.
- 2) Patients with Clinical Frailty Score (*CFS*) ≥ 3 (managing well) and < 7 (8 = very severely frail, approaching end-of-life or 9 = terminally ill) at time of acceptance for cardiac surgery.
- 3) Patients with an estimated ≥ 4 week wait time.

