3.5.3 Randomization

Trial Randomization using *REDCap*: The Randomization Module within *REDCap* allows researchers to randomly assign participants to specific groups. [name] has experience and will be responsible for study randomization. Assessors of pre- and post-operative data will be blinded to treatment group allocation.(47)

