5.2 Statistical/Analytical Plan

Objective 1: To determine if *Prehab* reduces the proportion of frail elderly patients requiring a prolonged hospital length of stay of >7 days. A univariable analysis will be undertaken to determine if hospital *LOS* > 7 days is associated with frailty and other patient-level factors. A stepwise multivariable logistic regression model will then be developed to determine if *Prehab* attendance is independently associated with a decreased risk of prolonged hospital length of stay > 7 days. As a secondary analysis, hospital *LOS* will also be compared as a continuous variable between the *Prehab* and standard care groups using a Mann-Whitney test.

“The PREHAB Study” (Pre-operative Rehabilitation for reduction of Hospitalization After coronary Bypass and valvular surgery.)

Objective 2: Does attending *Prehab* influence frailty, exercise capacity, physical activity behavior, in-hospital complications, and *HRQoL*? Although we will employ four different measures of frailty, based on our preliminary data and based on a Task Force’s position statement(90), the Modified Fried Criteria will be the primary frailty outcome over time from baseline to the end of *Prehab* program (pre-operatively), or from baseline to the 3-month post-operative follow-up. The primary measure of exercise capacity will be the *6MWT* and will be analysed with univariable linear regression models to evaluate the association between the *6MWT* and *Prehab* attendance. Accelerometers will be used to objectively measure the number of minutes spent performing moderate to vigorous physical activity (*MVPA*) and total physical activity (*TPA*) per day for a period of 7 days and compared between groups. A composite outcome for a major adverse cardiac event (i.e. *MACCE* = in-hospital stroke, myocardial infarction, renal failure requiring dialysis and death) and delirium will be compared between groups using a Chi-Square or Fisher’s Exact test. A multivariable logistic regression will be used to identify if *Prehab* is independently associated with in-hospital delirium. The *SF-12v2* and *EQ-5D* scores, after normative standardization, will be analyzed through use of a repeated *ANOVA* to allow for a standardized group and group/time interaction effect estimation.

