Appendix II - Five item Geriatric Depression Scale (5-GDS)

Five item Geriatric Depression Scale

VII. MOOD		
7.1 Are you basically satisfied with your life?	 Yes	 No
7.2 Do you often get bored?	 Yes	 No
7.3 Do you often feel helpless?	 Yes	 No
7.4 Do you prefer to stay at home rather than going out and doing new things?	 Yes	 No
7.5 Do you feel pretty worthless the way you are now?	 Yes	 No

Clinical Rehabilitation

<http://cre.sagepub.com/>

Prehabilitation program for elective coronary artery bypass graft surgery patients: a pilot randomized controlled study

[name], [name], [name], [name], [name], [name], [name], [name] and [name]
Clin Rehabil published online 23 January 2014
DOI: 10.1177/0269215513516475

The online version of this article can be found at:

<http://cre.sagepub.com/content/early/2014/01/22/0269215513516475>

Published by:

<http://www.sagepublications.com>

Additional services and information for *Clinical Rehabilitation* can be found at:

Email Alerts: <http://cre.sagepub.com/cgi/alerts>

Subscriptions: <http://cre.sagepub.com/subscriptions>

Reprints: <http://www.sagepub.com/journalsReprints.nav>

Permissions: <http://www.sagepub.com/journalsPermissions.nav>

[>> OnlineFirst Version of Record - Jan 23, 2014](#)

[What is This?](#)

Prehabilitation program for elective coronary artery bypass graft surgery patients: a pilot randomized controlled study

Clinical Rehabilitation
1–10
© The Author(s) 2014
Reprints and permissions:
sagepub.co.uk/journalsPermissions.nav
DOI: 10.1177/0269215513516475
cre.sagepub.com

**Jo-Ann V Sawatzky¹, [name]^{2,3},
A Elizabeth Ready², Neal Lerner⁴, Sue Boreskie⁴,
Darlene Lamont⁴, Dean Luchik⁴, Rakesh C Arora⁵ and
[name]^{2,3,6}**

Abstract

Objective: To determine the feasibility of a cardiac prehabilitation (Prehab) program for patients waiting for elective coronary artery bypass graft (CABG).

Design: A two-group parallel randomized controlled trial.

Setting: Medical fitness facility.

Subjects: Seventeen preoperative elective CABG surgery patients were randomized to standard care ($n = 9$) or Prehab ($n = 8$).

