Patients in the Prehab group attended a mean \pm SD 19 ± 7 exercise sessions over a mean exposure time of 8.2 ± 2.2 weeks. Based on chart reviews at the medical fitness facility after Prehab completion, no adverse events occurred during participation in the Prehab program. Neither surgery parameters nor prevalent postoperative complications differed between the two groups (Table 1).

No differences were observed at baseline for total distance walked on the 6MWT between the standard care and Prehab groups (Table 2). In contrast, compared with baseline, participants in Prehab walked significantly further preoperatively and three months postoperatively ($p < 0.05$) than standard care. Similarly, baseline gait speeds (Table 2) between the standard care and Prehab groups were non-significant. Over time, standard care participants did not improve gait speed preoperatively or three months postoperatively. However, in the Prehab group, an interaction effect was observed ($p < 0.05$), where gait speed was improved preoperatively and three months postoperatively, respectively, as compared with the standard care group.

We attempted to capture accelerometer data at all time points (i.e. baseline, preoperatively, and three months postoperatively); however, 11 of 15 participants in the study had their surgeries within 1–3 days of receiving notification, which was less than the minimum required accelerometer wear time of 4 days. Based on this limitation, we analyzed accelerometer data for the baseline and three month postoperative time points only (Table 3). When physical activity was assessed in 10-minute bouts, no differences were found for any intensity of physical activity at any time. Additionally, no differences between groups were observed when physical activity was analyzed in sporadic bouts for TotalPA_{spor} at any time. However, a main effect of time was observed for both groups, where

Table 1. Comparison of baseline characteristics and surgery parameters between groups.

	Standard care (n = 7)	Prehab (n = 8)	p-value
Demographics			
Age (years)	63 ± 9	64 ± 7	0.63
Gender (% female per group)	1 (14%)	2 (25%)	0.99
Height (cm)	172.6 ± 6.1	173.0 ± 11.7	0.79
Weight (kg)	89.4 ± 6.2	94.1 ± 15.5	0.46
BMI	30.0 ± 2.7	31.5 ± 4.4	0.43
Preoperative summary			
Ejection fraction	62% ± 10%	58% ± 11%	0.51
CCS class angina score*	2 (1–3)	2 (1–3)	1.00
Previous MI	4 (57%)	4 (50%)	1.00
Arrhythmia	3 (43%)	2 (25%)	1.00
Hypertension	6 (86%)	6 (75%)	1.00
CVA/TIA	1 (14%)	1 (13%)	1.00

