participants. Over the past decade, length of stay following elective cardiac surgery has declined from an average seven days to five days,²² which coincides with the average length of hospital stay in our study. Therefore, recent advances in surgical procedures, as well as a small sample size in the current study, could account for the differences observed in our study, as compared with the cardinal study by Arthur et al. published in 2000, where they found a reduction in the length of hospital stay of one day.

Our data shows that all eight (100%) of the Prehab patients chose to enroll in cardiac rehabilitation postoperatively, which was significantly different from the three (43%) standard care patients who chose to enroll. These data add to the previous literature, where Arthur et al.⁸ found that CRP attendance rates postoperatively were 70% among Prehab participants, and only 57% among standard care participants. Collectively, a Prehab intervention for elective CABG surgery patients could enhance CRP attendance postoperatively because current estimates indicate that only 15%–20% of North Americans of the referred cardiac population chooses to enroll.²³ However, we acknowledge that only 29% of the eligible elective CABG surgery patients who were contacted chose to participate in the study (Figure 1).

This pilot study has several limitations. The research assistant was not blinded to which participants were in each group, thus increasing detection bias. However, data collection by the research assistant was conducted in accordance with standardized procedures for each outcome variable. In the context of generalizability, beta-blocker use was significantly higher in the standard care group compared with the Prehab group. Furthermore, our recruitment criteria limited us to 79/297 (27%) of the elective CABG surgery cohort. We also did not recruit patients scheduled for other surgeries (i.e. valve repair/replacement, combination surgeries); however, this was a safety feature of our study based on the consensus of cardiac surgeons and cardiologists at the hospital site, that the lack of supportive evidence concerning the safety of a Prehab intervention warranted the exclusion of more complex procedures.

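### Planned procedure should be a fixed term in the primary length-of-stay model, because the trial extends Prehab from CABG-only evidence to valve and combined surgery

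*Combined protocol and SAP*

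**What the plan says.** **Evidence base.** Section 3.1 describes the earlier preoperative trial as enrolling "249 low-risk patients awaiting elective" CABG. The pilot abstract reports that "Seventeen preoperative elective CABG surgery patients were randomized to standard care" or Prehab. Its discussion states: "We also did not recruit patients scheduled for other surgeries (i.e. valve repair/replacement, combination surgeries". It calls this a safety feature agreed by surgeons and cardiologists at the hospital site, on the ground that "the lack of supportive evidence concerning the safety of a Prehab intervention warranted the exclusion of more complex procedures".

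**Present trial.** Section 3.3.1 admits isolated CABG, "aortic valve repair/replacement for moderate aortic stenosis or severe regurgitation", mitral valve surgery, and combined CABG/valve procedures.

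**Use of procedure.** Sections 3.4.1 and 3.4.9 list procedure data among the items collected. For the primary outcome, section 5.2 screens frailty and unnamed patient-level factors one at a time, after which "A stepwise multivariable logistic regression model will then be developed". No covariate is guaranteed a place. Section 3.5.3 says that the REDCap module "allows researchers to randomly assign participants to specific groups" and names no stratification factor. Section 4 sends all adverse events to the DSMB without saying how they will be tabulated.

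**The concern.** Type of operation is a plausible prognostic factor for postoperative stay. It is also the respect in which this population most plainly departs from the two trials behind the intervention. A baseline factor of that kind should be in the primary model by prior decision.

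Under section 5.2 its inclusion depends on how strongly it happens to be associated with the outcome in this sample. Stepwise selection does not look at whether the arms are balanced on it. A chance imbalance could therefore go uncorrected, and the covariates behind the headline estimate would be known only after the outcomes had been seen. Some precision, a bias-free comparison conditional on the observed case mix, and a fixed analysis are at stake.

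**Working it through.** **1. The plan's own figure.** Inputs from section 5.3: 58.3% against 38.3%, two-sided alpha 0.05, power 80%, 1:1 allocation, 20% dropout. With mean proportion 0.483 and pooled variance under the null:

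n = [1.960 × √(2 × 0.483 × 0.517) + 0.842 × √(0.583 × 0.417 + 0.383 × 0.617)]² / 0.20² = 96.8, so 97 per arm and 194 in all.

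97/0.8 = 121.25, so 122 per arm and 244 in all. Power at 97 per arm is 80.1%. The stated figures reproduce, and nothing below changes them.

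**2. Share of patients having the newly admitted operations.** Table 5, frail column (n = 72): isolated CABG 39, isolated valve 17, CABG plus valve 13, other 3. Section 3.3.1 does not admit the other operations, so they are left out:

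(17 + 13)/69 = 43.5%

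That is about 106 of 244 patients, or 53 of 122 in the Prehab arm. It assumes that the cohort's mix applies here. The trial excludes severe stenosis and the cohort is not described as doing so, so the true share could be lower.

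**3. Chance of imbalance if allocation is unstratified.** Randomisation acts on 122 per arm. With q = 0.435, the standard deviation of the between-arm difference in share is √(2 × 0.435 × 0.565/122) = 0.0635. The probability of a difference of 10 points or more is then:

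| Method | Probability |
|---|---|
| Normal approximation | 11.5% |
| Two independent binomials | 10.6% |
| Hypergeometric (106 of 244) | 9.3% |

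This gives about 9% to 12%.

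**4. What such an imbalance would do.** Shift in the crude difference = imbalance × risk difference D between procedure groups. The documents give no value for D, so 10, 20 and 30 points are assumed:

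- 0.10 × 0.10 = 1 point
- 0.10 × 0.20 = 2 points
- 0.10 × 0.30 = 3 points

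The design target is 20 points.

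**5. What adjustment would gain.** Share of outcome variance explained: R² = D² × q(1 − q)/(0.483 × 0.517), with q(1 − q) = 0.2457 and denominator 0.2497. Power = Φ[(0.842 + 1.960)/√(1 − R²) − 1.960].

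| Assumed D | R² | Power at 97 per arm |
|---|---|---|
| 10 points | 0.010 | 80.4% |
| 20 points | 0.039 | 81.6% |
| 30 points | 0.089 | 83.5% |

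This is a linear approximation to a logistic analysis, adequate for showing the order of magnitude.

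**The case against.** **No evidence that procedure drives stay.** No table reports stay by procedure. Tables 5 and 6 show frail patients with more isolated CABG than non-frail patients (54.2% against 42.6%) and yet more stays beyond 7 days (58.3% against 37.7%). A reader might set the pilot's mean stays of 5.3 and 5.1 days against the mixed-procedure cohort and conclude that procedure is a major determinant. The documents do not support that: the pilot completers numbered 15, were younger (means 63 and 64, against 68.7 in the non-frail cohort) and were selected differently. This objection stands, which is why D above is an assumption.

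**Small effects.** Even on those assumptions the shift is 1 to 3 points and the power gain at most about 3.5 points. This also stands; the case for the change is that it costs almost nothing.

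**Safety is already guarded.** A reader might infer that valve patients are exposed without protection, or that pooled counts will conceal harm. Section 3.3.2 excludes severe aortic or mitral stenosis and outflow obstruction. Prehab patients have a supervised graded stress test (3.5.5.4.2), a medical director oversees every case (3.5.2), and stability is checked twice weekly (section 4). The DSMB's terms of reference were still to be drafted (9.2), so the reporting format is unknown. The pilot's caution can also be read as being about an untested programme in general.

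**Stratification is inferred from silence.** Section 3.5.3 neither states nor rules out strata, and Figure 4 is not available. Crossing two procedure groups with five sites gives ten strata. Two sites start one and two years late (8.7), so some strata would be sparse, and small blocks in an open trial make allocation easier to guess. This stands against requiring stratification.

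**Why procedure rather than site or frailty?** The weakness of stepwise selection applies to any covariate. That is true, but procedure has a particular claim here because it marks the extension beyond the earlier evidence.

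**Conclusion.** The point holds as an improvement to the primary analysis. A baseline factor that separates this population from the CABG-only evidence is already collected, but its place in the model is left to a data-driven rule. Pre-specifying it is better than the stated rule whatever the data show.

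The size is modest: a shift of 1 to 3 points avoided in the roughly 9% to 12% of unstratified allocations with a 10-point imbalance or worse (more if the imbalance is larger), and power of 80.4% to 83.5% in place of about 80%. Both rest on an assumed 10- to 30-point risk difference and on the frail cohort's procedure mix.

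Three stronger conclusions are not supported. The sample size is not wrong. Procedure has not been shown to determine stay. The plan has not been shown to be unsafe for valve patients or to use simple randomisation. Using 97 per arm as the base would put the chance of imbalance at about 16%, but allocation is made on the 122 per arm randomised. Which operations should be eligible is a clinical question and is not judged here.

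**What to change.** In section 5.2, Objective 1, state that the primary logistic model for stay beyond 7 days contains two pre-specified fixed terms, kept outside any selection step:

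- randomised arm, consistent with the intention-to-treat design in section 3.2 and replacing the present reference to attendance;
- planned procedure, as isolated CABG against valve or combined.

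Procedure should be coded as planned at acceptance for surgery, so that it is a true baseline value. The cost is one sentence and one degree of freedom. No new data are needed, the sample size is unchanged, and the change can still be made after recruitment has begun, provided that it precedes unblinded analysis.

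Optional: when the DSMB's terms of reference are drafted, ask for adverse events by arm within the two procedure groups, at the cost of one extra table split. Stratifying the REDCap randomisation by procedure is also possible but not required; the steering committee would need to weigh sparse strata at the late-starting sites and predictability in an open trial. If either provision already exists in material not shown, stating it in section 4 or 3.5.3 is enough.
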